9.4.3 Method of Assigning Subjects to Treatment

At Screening Visit 2 (baseline assessment), authorized site personnel will use the IRT system to randomize the subject. The randomization program will assign the subject to a double-blind treatment group and will assign a bottle number that corresponds to the assigned treatment group. Subjects will be randomized to either sarecycline or placebo in a 1:1 ratio using block randomization. At Visit 1, Visit 2 and Visit 3, site personnel will again use the IRT system to dispense subsequent bottles associated with the assigned treatment group. Only bottle numbers provided by the IRT should be dispensed to subjects.

The randomization schedule will be prepared by a statistician not involved with this study (e.g., an independent, randomization statistician) using SAS® PROC PLAN.

9.4.3.1 Subjects Participating in PK Schedule 3

Subjects who participate in PK Schedule 3 will receive one dose of active study treatment at Visit 4 (Week 12) regardless of randomized study treatment (active or placebo).

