11.4.3 Missing Data Handling for Co-Primary and Secondary Endpoints

For the co-primary and secondary efficacy analyses, the primary missing data imputation method is multiple imputation (MI), as outlined in the following procedures:

- The SAS PROC MI procedure with a fully conditional specifications (FCS) method will be used to create 20 imputations. The FCS is proposed as it allows for accommodation of categorical variables and it has the versatility to handle arbitrary missing data patterns. Based on these 20 imputations, the relative efficiency will be 0.995 for 10% of missing data and 0.990 for 20% of missing data (Rubin, 1976, 1987, 1996).
- For inflammatory lesion counts, if any of the subtypes (papules, pustules, and nodules/cysts) is missing, the inflammatory lesion count is missing. The variables included in the imputations are age, sex, and the raw measurements of the corresponding endpoint counts at baseline, Week 3, Week 6, Week 9, and Week 12
- For IGA, the raw scores will be used for the imputation. The variables included in the imputations are age, sex, and the measurements of the endpoint at baseline, Week 3, Week 6, Week 9, and Week 12
- All imputations will be performed by treatment group based on the randomized study medication. The number of imputations is set at 20 with number of 50 burn-in iterations. The seed used for imputation for all endpoints is █. For IGA raw scores and lesion counts, regression with predictive mean matching method will be used. The imputed values will be rounded to the nearest integer.
- An analysis of covariance (ANCOVA) model for continuous endpoints (inflammatory lesion counts) will be performed for each of the imputed datasets.
- A Cochran-Mantel-Haenszel (CMH) analysis for the binary endpoint (IGA success) will be performed for each of the imputed datasets.
- The SAS PROC MIANALYZE procedure will be used to produce final parameter estimates, including the point estimates and standard errors, adjusted treatment differences, confidence intervals and p-values for the primary and secondary variables.
- For the CMH test, the Wilson-Hilferty transformation (Wilson & Hilferty, 1931, O'Kelly & Ratitch, 2014) will be used. Under the null hypothesis, the transformed statistic is approximately normally distributed:

$$wh_CMH^{(m)} = \sqrt{\frac{cmh^{(m)}}{k}} \sim normal(1 - \frac{2}{9k}, \frac{2}{9k})$$

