The study includes a screening period of up to 35 days to establish eligibility and baseline conditions followed by a 12-week treatment period. Eligible subjects will be randomized in a 1:1 ratio to receive daily oral doses of either 1.5 mg/kg sarecycline tablets or placebo tablets. Subjects will return to the clinic on an outpatient basis following 3, 6, 9 and 12 weeks of treatment. At each clinic visit, facial acne will be evaluated through lesion counts and Investigator's Global Assessment (IGA) scores by visual inspection; non-facial inflammatory acne will also be evaluated by IGA of the neck, chest and back. The co-primary efficacy endpoints of the study are the absolute change from baseline in the facial inflammatory lesion count at Week 12 and a dichotomized IGA (dichotomized to reflect either 'success' or 'failure' with 'success' defined as at least a 2-point decrease from baseline in the IGA assessment and a score of clear [0] or almost clear [1] on the IGA assessment) at Week 12. Safety evaluations (adverse events, vital signs, clinical laboratory evaluations, electrocardiograms (ECG) and physical examinations) will be conducted at specific treatment period visits and at study termination.

The study drug, referred to as investigational product in this statistical analysis plan, quantity and dispensing schedule for this study are as follows:

Visit	Quantity Dispensed
Screen Visit (SV) 2	30
1	30
2	30
3	30

The schedule of evaluations for Study SC1401 is presented in Table 4-1.

Table 4–1. Study Schedule of Events: Study SC1401

	Screening Period		Treatment Period					
	SV1	SV2 (Baseline Assessment)	Telephone Contact Week 1 ± 3 d	Visit 1 Week 3 ± 3 d	Visit 2 Week 6 ± 3 d	Visit 3 Week 9 ± 3 d	Visit 4 Week 12 /ET ± 3 d	Visit 5 ^d Week 13 /ET ± 3 d
Informed Consent	X							
Assign Subject Number using the IRT	X							
Inclusion/Exclusion	X	X						
Demographic Data	X							
Medical/Surgical History	X							
Physical Examination	X	X ^a					X	X
Height & Weight	X	Weight only					Weight only	Weight only
Vital Signs	X	X		X	X	X	X	X
Hematology, Serum Chemistry, Urinalysis and Lipids	X	X ^b		X			X	
TSH, Free T4 and T3	X						X	
Urine pregnancy test	X	X		X	X	X	X	X
ECG	X						X	
Facial Investigator's Global Assessment		X		X	X	X	X	
Facial Lesion Counts		X		X	X	X	X	
Facial Photographs		X		X	X	X	X	
Non-facial Investigator's Global Assessment		X		X	X	X	X	

Table 4–1. Study Schedule of Events: Study SC1401

	Screening Period		Treatment Period					

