10.0 EFFICACY ANALYSES

The efficacy analyses will be based on the ITT Population. All summaries on this population will be based on the investigational product each subject was randomized to receive. The multiple imputation (MI) approach will be used to impute missing values for co-primary and secondary efficacy analyses and details are further described in Section 16.2. Sensitivity analyses for efficacy parameters will be performed using alternative approaches to handle missing data, as well as an observed cases (OC) approach using the PP population. *Baseline* for efficacy is defined as the last non-missing efficacy assessment before the first dose of the investigational product. All statistical tests will be 2-sided hypothesis tests performed at the 5% level of significance for main effects. All confidence intervals will be 2-sided 95% confidence intervals, unless stated otherwise.

The descriptive statistics for all the continuous variables will include the mean, median, 25th percentile, 75th percentile, standard deviation (SD), standard error of mean (SEM), minimum, maximum, and number of subjects. Descriptive summaries will be provided for raw, change from baseline (CFB), and %CFB values for continuous efficacy endpoints. Frequency distributions for all the categorical variables will be presented as counts and percentages. Summaries will be provided by visit and treatment, as appropriate.

While every effort will be made to randomize a sufficient number of subjects at each study site, in the event that this is not possible, study sites may be pooled for statistical inference testing. Study sites (centers) will be pooled by geographical location based on region definitions from the US Census Bureau (Northeast, Midwest, South, and West; US Census Bureau, 2013) for analysis purposes so that in each pooled site the number of subjects is reasonably large and consistent in size between pooled sites. Sites within a geographic location will be pooled starting with the sites that have the lowest number of randomized subjects pooled together such that the pooled site has a minimum of 12 randomized subjects after pooling.

The sites to be pooled for each geographic location will be documented in a signed memo prior to unblinding of the treatment code. A list of sites and the corresponding pooled sites will be presented.

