- For inflammatory lesion counts, if any of the subtypes (papules, pustules, and nodules/cysts) is missing, the inflammatory lesion count is missing. The variables included in the imputations are age, gender, and the measurements of the corresponding endpoint count) at baseline, Week 3, Week 6, Week 9, and Week 12.
- For IGA, the raw scores will be used for the imputation. The variables included in the imputations are age, gender, and the measurements of the endpoint at baseline, Week 3, Week 6, Week 9, and Week 12.
- All imputations will be performed by treatment group based on the randomized study medication and based on the randomized gender strata. The number of imputation is set at 20 with number of 50 burn-in iterations. The seed used for imputation for all endpoints is [REDACTED]. The logistic regression model for gender is based on the probability of female. For age, IGA raw scores and lesion counts, regression with predictive mean matching method will be used. The imputed values will be rounded to the nearest integer for IGA and lesion counts.
- The following are the SAS programs used to impute IGA at week 12:

The following SAS program will be used to impute inflammatory and non-inflammatory lesion counts at week 12.

- An analysis of covariance (ANCOVA) model for inflammatory lesion counts and a CMH analysis for the IGA success as stated in Sections 10.1.1 and 10.1.2, respectively, will be performed for each of the imputed dataset.
- An analysis of covariance (ANCOVA) model for inflammatory and non-inflammatory lesion counts as stated in Section 10.2 will be performed for the imputed dataset for the secondary endpoints.
- The SAS PROC MIANALYZE procedure will be used to produce final parameter estimates, including the point estimates and standard errors, adjusted treatment differences, confidence intervals and p-values for the primary and secondary variables.
- For the CMH test, the Wilson-Hilferty transformation (Wilson & Hilferty, 1931, O'Kelly & Ratitch, 2014) will be used. Under the null hypothesis, the transformed statistic is approximately normally distributed:

$$wh_CMH^{(m)} = \sqrt[3]{\frac{cmh^{(m)}}{k}} \sim normal\left(1 - \frac{2}{9k}, \frac{2}{9k}\right)$$

Where $cmh^{(m)}$ is the chi-square statistics each with k degrees of freedom from $m = 1, \dots, M$ imputed datasets. In this case, $k=1$. This statistic will be passed to PROC MIANALYZE to obtain the combined p-value for CMH test.

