16.9 CHARACTER VALUES OF CLINICAL LABORATORY PARAMETERS

If the reported value of a clinical laboratory parameter cannot be used in a statistical summary table because, for example, a character string is reported for a parameter of the numeric type, a coded value must be appropriately determined for use in the statistical analyses. The actual values, however, as reported in the database will be presented in the data listings.

Table 16.9–1 shows examples of how some possible laboratory results should be coded for the analysis.

Table 16.9–1. Examples of Coding Special Character Values for Clinical Laboratory Parameters

Laboratory Test, SI Unit	Possible Laboratory Results	Coded Value for Analysis
CHEMISTRY		
ALT, U/L	< 5	0
AST, U/L	< 5	0
Bilirubin, total, $\mu\text{mol/L}$	< 2	0
URINALYSIS		
Glucose, mmol/L	= OR $> 55, \geq 55, > 0$	Positive
	≤ 0 , negative	Negative
pH	$> 8.0, \geq 8.0$	8.0
	≥ 8.5	8.5
Protein	= OR $> 3.0, \geq 3.0, > 0$	Positive
	≤ 0	Negative

ALT = alanine aminotransferase; AST = aspartate aminotransferase; SI = *Le Système International d'Unités* (International System of Units).

17.0**CHANGES IN AMENDMENT 1 OF THE STATISTICAL ANALYSIS PLAN**

Rationale: This SAP, Amendment 1 is being updated prior to database lock to allow for the non-inflammatory lesion count assessment to be considered as a secondary efficacy endpoint. It will be included in the hierarchy of testing of the secondary endpoints to maintain type 1 error control at 0.05. Since this change is occurring after the completion of all patients in the study, and given that there is no impact on patient safety or study conduct, the protocol will not be amended to reflect this change.

Summary of changes: Sections 10.2, 11.5.1, and 16.2 have been updated to add non-inflammatory lesion count changes from baseline as a secondary efficacy endpoint and to reflect the dual nature of this parameter as being evaluated both for efficacy and for safety.

18.0

REFERENCES

Littell, R. C., Milliken, G. A., Stroup, W. W., Wolfinger, R. D., and Schabenberger, O. (2006), *SAS for Mixed Models*, Second Edition, Cary, NC: SAS Press.

Rubin, DB. Inference and missing data. *Biometrika*. 1976;63:581-592.

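### Does imputing within gender strata that only SAP 16.2 mentions leave the primary imputation model open?

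*SAP*

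**What the plan says.** Protocol 11.4.3 sets the grouping for the primary imputation: "All imputations will be performed by treatment group based on the randomized study medication". Sex and age are model variables, together with the endpoint at baseline and at each visit.

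SAP 16.2 uses nearly the same sentence with an addition: "All imputations will be performed by treatment group based on the randomized study medication and based on the randomized gender strata". In the same section the variable list still contains gender (for IGA: "The variables included in the imputations are age, gender, and the measurements of the endpoint at baseline", and at the later visits), and a method is named for it: "The logistic regression model for gender is based on the probability of female".

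On allocation, Protocol 9.4.3 says "Subjects will be randomized to either sarecycline or placebo in a 1:1 ratio using block randomization". SAP 4.0 says "Eligible subjects will be randomized in a 1:1 ratio to receive daily oral doses of either 1.5 mg/kg sarecycline tablets or placebo tablets". Neither names a stratification factor, and neither rules one out.

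Two statements bear on which text governs. Protocol section 11 leaves the detailed statistical methods to a SAP finalised before database lock. SAP 4.0 describes the SAP as the more technical elaboration of the protocol. SAP 16.2 also announces SAS programs for imputing IGA and lesion counts at Week 12; they do not appear in the public copy.

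**The concern.** Multiple imputation is the primary missing-data method for both co-primary endpoints and all secondary endpoints, so its grouping rule is part of the primary analysis. Read literally, the two documents describe different models. The protocol fits one model per arm, with sex shifting the mean. The SAP fits one per arm and gender, so every coefficient and the pool of donors for predictive mean matching become gender-specific.

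Two things make the SAP wording look unreliable. It refers to strata set at randomisation that are described nowhere else. It also asks for gender as a predictor inside cells where gender cannot vary. The summary of SAP Amendment 1 (section 17.0) mentions no change of grouping.

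If the text really left two groupings open, an analyst could choose between them after unblinding. The plan fixes the seed, the 20 imputations and the 50 burn-in iterations, which is meant to prevent that kind of choice.

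**Working it through.** **1. The plan's own figure.** The only number given for this imputation is its relative efficiency, 1/(1 + γ/m) with m = 20. At γ = 0.10 it is 1/1.005 = 0.995; at γ = 0.20 it is 1/1.010 = 0.990. Both match the plan, and neither depends on the grouping.

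**2. Are the finer cells large enough?** The plan has 500 subjects per arm. The documents do not give the female share, so I assume 40% to 60%. Each arm-by-gender cell then holds 500 × 0.4 = 200 to 500 × 0.6 = 300 subjects. With 10% to 20% missing (also an assumption), observed donors number from 200 × 0.8 = 160 to 300 × 0.9 = 270. The Week 12 regression within a cell has an intercept, age, baseline and three visits, so six coefficients. In the smallest cell that leaves 160/6, about 27 observed subjects per coefficient. The models can be fitted.

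**3. Is either grouping unsound?** Separate regressions by gender contain the protocol's model as a special case, in which the slopes happen to be equal. Grouping by gender therefore drops no information that the protocol's model uses. Both groupings depend only on randomised arm and a characteristic recorded at screening.

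**4. The internal redundancy.** Within a gender cell, gender has variance 0 and adds nothing as a predictor. The logistic model for gender would matter only if gender were missing, and it is collected with the demographic data at the first screening visit. SAP 16.2 names an imputation method for age as well, so the sentence reads as a declared method for every listed variable.

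**5. How far do the results differ?** The assumptions of the simulation were: 500 per arm; 50 sites of 20; Week 12 change SD about 12; realised difference about 2.7 lesions; IGA success about 28% v 12%; monotone dropout at random of 10% or 20%; a sex effect of 0 lesions (50% female) or 3 lesions (60% female); predictive mean matching with 5 donors; 20 imputations; 200 trials in each of four scenarios.

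| Comparison | Lesions | IGA success |
|---|---|---|
| Mean shift between groupings | at most 0.013 | at most 0.03 points |
| Within-trial shift between groupings, 95th percentile | 0.13–0.21 (0.18–0.26 SE) | 0.4–0.6 points (0.16–0.23 SE) |
| Same model, new seed, 95th percentile | 0.12–0.21 | 0.4–0.5 points |

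The SE ratio between groupings was 0.997 to 1.002.

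**6. How often would a verdict change?** Under the plan's lesion assumptions (difference 3, SD 12), expected z = 3/(12 × √(2/500)) = 3.95. Treat the shift as normal and independent of z, with SD equal to its 95th percentile divided by 1.96:

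- 0.18/1.96 = 0.092 and 0.26/1.96 = 0.133.
- The mean absolute shift is 0.798 times the SD: 0.073 and 0.106.
- The normal density of z at the threshold is φ(3.95 − 1.96) = 0.055.
- The chance of a changed verdict is about 0.055 × 0.073 = 0.4% to 0.055 × 0.106 = 0.6%.

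As a harsher case, let 20% of subjects contribute nothing. Then z = 3/(12 × √(2/400)) = 3.54, the density is 0.115, and the larger shift gives 0.115 × 0.106 = 1.2%.

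For IGA (23% v 10%), z = 0.13/√((0.23 × 0.77 + 0.10 × 0.90)/500) = 5.62 and the density is about 0.0005. The chance is below 0.01%.

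**The case for a change.** The strongest case for acting is that this is the primary analysis, that the added phrase cannot be traced to any described design feature, and that correcting it would take one sentence. A pre-specified analysis should be reproducible from its text, and here a reader cannot follow the prose literally. A shift of 0.26 SE can also matter: from z = 1.96 it reaches z = 2.22 (p = 0.026) one way and z = 1.70 (p = 0.089) the other.

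The point about wording stands. The rest is weaker. The p-value range places a 95th-percentile shift exactly at the threshold. Under the plan's assumptions only Φ(−1.73) − Φ(−2.25) = 3.0% of trials fall between those limits, and most of those would keep their verdict. The freedom to choose is not established either: the SAP prose gives one grouping, and the programs it announces would be expected to show how that was coded. Their absence from the public copy cannot be held against the plan. Silence about strata in Protocol 9.4.3 is weak evidence, because that section does not give the block size either. The SAP phrase may be the only public trace of a real stratum.

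The split does leave fewer donors in each cell. However, predictive mean matching draws on all observed subjects in a cell, here about 160 to 270, and no harm from the smaller pool was shown.

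**Conclusion.** No change follows. SAP 16.2 contains a loose phrase and a redundant predictor, both of which an analyst holding the randomisation record and the imputation programs can settle without judgement about the results. Either grouping gives a sound analysis. The simulation showed no bias of practical size, essentially equal standard errors, and within-trial movement of the same order as an arbitrary change of seed. No inflation of type I error was shown.

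The expected rate of changed lesion verdicts is about 0.4% to 0.6%, and about 1.2% if a fifth of the information is lost; for IGA success it is negligible. These rates assume the plan's effect sizes and a normal shift independent of z. The simulation behind the shift used assumed dropout, female share and sex effects, and its realised effects (about 2.7 lesions; 28% v 12%) differ somewhat from the plan's (3 lesions; 23% v 10%). What the documents cannot settle is whether gender was in fact a randomisation stratum, but the imputation is acceptable whichever is true.

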16.3 REPEATED OR UNSCHEDULED ASSESSMENTS OF SAFETY PARAMETERS

If a subject has repeated assessments before the start of investigational product, the results from the final nonmissing assessment made before the start of the investigational product will be used as baseline. If end-of-study assessments are repeated or if unscheduled visits occur, the last nonmissing postbaseline assessment will be used as the end-of-study assessment for generating summary statistics. However, all postbaseline assessments will be used for PCS value determinations, and all assessments will be presented in the data listings.

16.4**MISSING DATE OF THE LAST DOSE OF INVESTIGATIONAL PRODUCT**

When the date of the last dose of the investigational product is missing for a subject in the Safety Population, all efforts should be made to obtain the date from the Investigator. If after all efforts are made it is still missing, the last available dosing record date will be used as the last dose date.

16.5**MISSING SEVERITY ASSESSMENT FOR ADVERSE EVENTS**

If severity is missing for an AE that started before the date of the first dose of the investigational product, an intensity of mild will be assigned. If severity is missing for an AE that started on or after the date of the first dose of the investigational product, an intensity of severe will be assigned. The imputed values for severity assessment will be used for the incidence summary; the values will be shown as missing in the data listings.

16.6**MISSING RELATIONSHIP TO INVESTIGATIONAL PRODUCT FOR ADVERSE EVENTS**

If the relationship to study treatment is missing for an AE that started on or after the date of the first dose of the investigational product, a relationship of related will be assigned. The imputed values for relationship to study treatment will be used for the incidence summary; the values will be shown as missing in the data listings.

16.7**MISSING DATE INFORMATION FOR ADVERSE EVENTS**

The following imputation rules only apply to cases in which the start date for AEs is incomplete (ie, partly missing).

Missing month and day

- If the year of the incomplete start date is the same as the year of the first dose of the investigational product, the month and day of the first dose of the investigational product will be assigned to the missing fields
- If the year of the incomplete start date is before the year of the first dose of the investigational product, *December 31* will be assigned to the missing fields
- If the year of the incomplete start date is after the year of the first dose of the investigational product, *January 1* will be assigned to the missing fields

Missing month only

- If only the month is missing, the day will be treated as missing and both the month and the day will be replaced according to the above procedure

Missing day only

- If the month and year of the incomplete start date are the same as the month and year of the first dose of the investigational product, the day of the first dose of the investigational product will be assigned to the missing day
- If either the year of the incomplete start date is before the year of the date of the first dose of the investigational product or if both years are the same but the month of the incomplete start date is before the month of the date of the first dose of the investigational product, the last day of the month will be assigned to the missing day
- If either the year of the incomplete start date is after the year of the date of the first dose of the investigational product or if both years are the same but the month of the incomplete start date is after the month of the date of the first dose of the investigational product, the first day of the month will be assigned to the missing day

If the stop date is complete and the imputed start date as above is after the stop date, the start date will be imputed by the stop date.

If the start date is completely missing and the stop date is complete, the following algorithm will be used to impute the start date:

- If the stop date is after the date of the first dose of the investigational product, the date of the first dose of the investigational product will be assigned to the missing start date
- If the stop date is before the date of the first dose of the investigational product, the stop date will be assigned to the missing start date

